2.2 Overall Study Design

This is a randomized, double-blinded, placebo-controlled multiple-dose phase II study to evaluate the safety, tolerability and efficacy of three dose levels of MSDC-0602K in subjects with non-alcoholic steatohepatitis (NASH).

Approximately 380 subjects will be randomized at 1:1:1:1 ratio to the following four treatment arms, and the drug is taken orally once per day for 12 months:

- MSDC-0602K 62.5 mg
- MSDC-0602K 125 mg
- MSDC-0602K 250 mg
- Placebo

Randomization will be stratified by:

- Presence of Type 2 diabetes mellitus (T2DM) (Yes/No)
- Use of Vitamin E \geq 400 IU (Yes/No)
- Fibrosis score (F1 vs. F2/F3)

This study will comprise a maximum 42-day Screening period, a treatment period of 360 days and a 14-day follow-up period. The total duration of the study for each subject will be up to 416 days, including follow-up.

The primary efficacy endpoint will be assessed at 12 months after randomization. Visits to the clinic will be at baseline, 1, 2, 3, 6, 9, and 12 months, with one follow-up visit at study day 374.

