2.3 Sample Size and Power

Each active treatment group will be compared with the placebo group at the two-sided 0.05 significance level; 85 subjects per arm provides approximately 80% power to detect a difference in the proportions of subjects achieving the primary efficacy endpoint of 39.5% in any MSDC-0602K group versus 20% response rate in the placebo group. These response rates are similar to effects reported after 18 months daily treatment with 45 mg pioglitazone (58% response) or placebo (17% response) in subjects with pre-diabetes or T2DM (Cusi 2014); after 96 weeks daily treatment with 30 mg pioglitazone (34% response) or placebo (19%) in non-diabetic adults with NASH in the PIVENS study (Sanyal 2010); and in the GOLDEN study, after 52 weeks daily

treatment with 120 mg elafibranor (32% response) or placebo (21%) in the subset of NASH subjects with a baseline NAS ≥ 4 (Ratziu 2016). Assuming 10% of subjects will not complete the 12-month assessment due to early dropout, 380 subjects will be randomized to the study. Sample size calculations were made using nQuery Advisor® (Statistical Solutions Ltd., Boston, MA, USA).

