6.2.3 Imputation for Primary Endpoint

Sensitivity analyses will be performed on the primary endpoint using two different imputation methods. The sensitivity analyses will include all subjects who were randomized and who received at least one dose of study drug. Two approaches will be used to impute or substitute missing response at 12 months. Post-baseline observations that have been excluded from the primary analysis due to biopsies taken more than 14 days after last dose of study drug will be treated as missing and imputed or substituted as well.

When using multiple imputation, missing baseline and/or post-baseline values needed to determine response at 12 months will be imputed multiple times to account for the uncertainty about the true values to impute. To this end, each of the four categorical variables underlying the response definition of the primary endpoint will be imputed if missing, using the following categories:

- Steatosis: 0, 1, 2, 3
- Lobular inflammation: 0, 1, 2, 3
- Ballooning: 0, 1, 2
- Fibrosis score: 0, 1, 2, 3, 4

Using the SAS[®] procedure PROC MI 10 imputed data sets will be generated. The regression model will be adjusted for the corresponding baseline values and will further use presence of diabetes mellitus, Vitamin E use ≥ 400 IU, age, and sex as covariates.

An example of the SAS[®] code to be used is below:

```
proc mi data= out=<output dataset> seed=1234 nimpute=10
  minimum=<...> maximum=<...> round=<...>;
var <12 months steatosis> <baseline steatosis>
  <12 months lobular inflammation> <baseline lobular inflammation>
  <12 months ballooning> <baseline ballooning>
  <12 months fibrosis score> <baseline fibrosis score>
  <presence of diabetes mellitus> <Vitamin E use  $\geq 400$  IU> <sex><age at baseline>;
run;
```

The 10 multiple imputed datasets will be used separately in the statistical analysis model and the resulting odds ratios and 95% CIs will be combined via Rubin's rules (using PROC MIANALYZE) to provide a global estimate of the odds ratio with a corresponding 95% CI and p-value.

As a second sensitivity analysis of the primary endpoint, subjects with missing response data at 12 months will be included as non-responders. Similar to above, this sensitivity analysis will include all subjects who were randomized and who received at least one dose of study drug.

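### The example PROC MI code treats the categorical histology scores as multivariate normal with unspecified limits and rounding; it should be replaced, together with adding treatment to the imputation model (low priority)

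*SAP*

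**What the plan says.** SAP 6.2.3 states that "each of the four categorical variables underlying the response definition of the primary endpoint will be imputed if missing", and lists 4 levels for steatosis, 4 for lobular inflammation, 3 for ballooning and 5 for fibrosis. It then gives a PROC MI call, labelled an example, with 10 imputations and the options "minimum=<...> maximum=<...> round=<...>". The call has no CLASS, FCS, MONOTONE or BY statement.

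The covariate sentence and the VAR list both contain baseline scores, diabetes, vitamin E use, age and sex. Neither contains treatment group, although the logistic model in SAP 7.8.1 does.

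Biopsies outside the on-treatment window are also imputed: observations excluded "due to biopsies taken more than 14 days after last dose of study drug will be treated as missing and imputed or substituted as well". The planning figure for missing data is in SAP 2.3: "Assuming 10% of subjects will not complete the 12-month assessment due to early dropout, 380 subjects will be randomized to the study".

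SAP 7.8.1 makes this sensitivity analysis (1). The primary analysis uses observed data, and sensitivity analysis (2) counts missing responses as non-response.

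**The concern.** The text describes categorical variables while the code describes a normal model whose draws are coerced to integers. That PROC MI defaults to multivariate normal when no method is named is general software knowledge; the SAP does not say it.

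Coercion matters because the scores have only 3 to 5 levels. If draws are held within 0 and the top score and then rounded, each end category gets a bin half as wide as a middle one. For ballooning the bins are 0 to 0.5, 0.5 to 1.5 and 1.5 to 2, so the middle is over-filled. Limits half a category wider make the bins equal, and clipping piles the tails onto the end categories. With the settings blank, the SAP does not fix which of these applies.

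Primary response needs a NAS fall of at least 2 points, including at least 1 point in ballooning or inflammation, so errors in these scores feed into imputed response. At stake is whether sensitivity analysis (1) gives a fair picture of missing data.

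**Working it through.** **Inputs from SAP 2.2 and 2.3.** "Each active treatment group will be compared with the placebo group at the two-sided 0.05 significance level"; "85 subjects per arm provides approximately 80% power"; "39.5% in any MSDC-0602K group versus 20% response rate in the placebo group"; allocation 1:1:1:1; 10% missing; 380 randomised.

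**The plan's own figures reproduce.**
- True difference: 39.5 − 20 = 19.5 points. Odds ratio: (0.395/0.605)/(0.20/0.80) = 2.61.
- Power with 85 per arm: Φ[(0.195√85 − 1.96√(2 × 0.2975 × 0.7025))/√(0.20 × 0.80 + 0.395 × 0.605)] = Φ(0.840) = 0.7996, matching the stated 80%.
- Randomised: 340/0.9 = 378, against 380 stated.

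The documents give no figure for the imputed difference.

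**Relation used.** With a fraction m missing completely at random, overall difference = (1 − m) × 19.5 + m × imputed difference.

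**Simulation assumptions (none from the documents).** Latent-normal scores with assumed thresholds, calibrated to 20% and 39.5% response; correlation 0.3 between scores and 0.5 from baseline to month 12; 150,000 generated per arm before the NAS ≥ 4 filter. Several dose patterns were tried, including only one active dose at 39.5% and a graded pattern. Age, sex, diabetes and vitamin E were left out; by randomisation they cannot carry the treatment effect. The discrete model draws scores from donors with the same baseline profile, standing in for a categorical regression.

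| Imputation model | Imputed difference (points) | Overall, 10% missing | Overall, 30% missing |
|---|---|---|---|
| Normal, limits and rounding, no treatment (as printed) | −0.6 to +0.6 | 17.5–17.6 | 13.5–13.8 |
| Discrete, no treatment | −0.1 to +0.1 | 17.5 | 13.6–13.7 |
| Normal, treatment added, redraw within 0 and top score | 11.1–11.5 | about 18.6 | about 17.0 |
| Normal, treatment added, half-category limits | 15.0–15.4 | 19.0–19.1 | 18.1–18.3 |
| Normal, treatment added, clipping | 17.7–18.0 | 19.3 | 18.9–19.0 |
| Discrete, treatment added | 19.1 | 19.4 (OR 2.60) | 19.3 |

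**Check by hand at 10% missing.**
- Treatment omitted: 0.9 × 19.5 + 0.1 × 0 = 17.55, a loss of 1.95 points whichever method is used.
- Treatment included, worst setting: 0.9 × 19.5 + 0.1 × 11.1 = 18.66, a loss of 0.84.
- Treatment included, best setting: 0.9 × 19.5 + 0.1 × 18.0 = 19.35, a loss of 0.15.

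The simulated 18.6 to 19.3 gives losses of 0.2 to 0.9 points.

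**Scores.** With redraw within 0 and the top score, treatment included and all doses at 39.5%, imputed ballooning 0/1/2 is 16/60/25% against 23/37/40% true. Imputed steatosis 3 is 11% against 20% true.

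**Robustness.** Varying the baseline-to-month-12 correlation from 0.3 to 0.7 left the redraw result at 11.5 to 12.6 points. Other assumed thresholds gave 13 to 14 with redraw, 16 to 17 with half-category limits and about 18 with clipping.

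**The case against.** The strongest reply is that the call is only an example with placeholders, the governing text already says categorical, and the effect is trivial. The standard error of the difference at 85 per arm is √[(0.20 × 0.80 + 0.395 × 0.605)/85] = 0.0685, or 6.9 points, so a 0.9-point loss is 0.9/6.9 = 0.13 standard errors. The primary analysis uses observed data, a non-responder analysis is also planned, and no decision is tied to this one.

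All of that stands on size, and it is why the priority is low. It does not remove the mismatch. Beyond the code, the text mentions only a regression model and names no categorical method. The blank settings alone can move the imputed difference between about 11 and 18 points once treatment is in the model. The omission of treatment is in the covariate sentence as well as the code, so it is not an artefact of the example.

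A reader might infer that limits and rounding are what shrink the treatment difference in this SAP, for instance from 19 points to about 12. The documents do not support that. A figure near 12 requires fitting within arm or treatment in the model, and SAP 6.2.3 has neither. Under the printed variable list a discrete model loses the difference just as completely.

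A reader might also carry the ballooning distortion over to NASH resolution, which requires ballooning 0. Multiple imputation is specified only for the primary endpoint, so that does not follow.

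**Conclusion.** The text and the example code of SAP 6.2.3 describe different methods, and the code as printed can distort the imputed scores. How much depends on settings the SAP leaves open. The near-total loss of the imputed treatment difference comes mainly from leaving treatment out of the imputation model; it costs about 2 points overall at 10% missing. Limits and rounding are a second, smaller fault that shows in the treatment difference only once the first is mended: about 11 to 18 points imputed against about 19.5, or 0.2 to 0.9 points overall at 10% missing. Late biopsies set to missing could raise the missing share and the loss with it.

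The sizes rest on assumed score distributions and data missing completely at random; the mismatch between text and code does not. The effect is confined to sensitivity analysis (1) of the primary endpoint. Low priority, but worth correcting.

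**What to change.** Replace the example code in SAP 6.2.3 so that it matches the text, as one change with two parts:

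1. Declare the four scores in CLASS and impute them with FCS LOGISTIC (cumulative logit), using FCS REGPMM where categories are sparse. Delete minimum=, maximum= and round=.
2. Add treatment group to the covariate sentence and the VAR list, or impute separately by arm.

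Part 1 alone leaves the imputed difference near zero (about 17.5 points overall at 10% missing). Part 2 alone leaves it at about 11 to 18 points.

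The cost is a few lines of SAP text and code, settled before unblinding for the final analysis. The downside is possible sparse-category fits. Imputing by arm would fit up to five fibrosis levels on about 95 × 0.9 ≈ 85 observed subjects, and SAP 8 itself expects vitamin E use to be highly unequal. The SAP should therefore state in advance when the matching fallback applies.

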6.2.4 Imputation for Missing Changes in Laboratory Values

HbA1c

Additional sensitivity analyses may be performed conditional on the distribution of changes in glycemic control medications between the placebo and active treatment groups at 6 and 12 months.

If more than 35% of the subjects who had a major up-titration of glycemic control medications are in the placebo group, a sensitivity analysis may be done where the 6- and 12-month values of HbA1c for subjects who had a major up-titration of glycemic control medications will be imputed to be 0.5 % higher than the observed value.

If more than 15% of the subjects who had a major down-titration of glycemetic control medications are in the placebo group, a sensitivity analysis may be done where the 6- and 12-month values of HbA1c for subjects who had a major down-titration of glycemetic control medications will be imputed to be 0.5 % lower than the observed value.

If more than 35% of the subjects missing paired change-from-baseline values of HbA1c (separately at 6 and 12 months) are in the placebo group, a sensitivity analysis may be performed where the missing follow-up value will be assigned the baseline value plus 0.5%.

Liver function tests and other markers

Additional sensitivity analyses may be performed conditional on the distribution of missing values between the placebo and active treatment groups at 6 and 12 months.

If > 35% of the subjects missing paired change-from-baseline values of the following laboratory tests (separately at 6 and 12 months) are in the placebo group, a sensitivity analysis may be performed where missing follow-up values will be assigned the corresponding baseline values plus 0.5 times the maximum change (maximum increase) from baseline for the parameter observed in any subject (i.e., regardless of treatment group) at the timepoint: ALT, AST, ALP, Total Bilirubin, GGT, pro thrombin time, APRI score, CK-18, ELF, FIB-4, Pro-C3, Fibro-test score, and HOMA-IR. Likewise for albumin, missing follow-up values may be assigned the corresponding baseline values minus 0.5 times the minimum change (maximum decrease) from baseline .

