7.6 Prior and Concomitant Medications

Medications received prior to or concomitantly with treatment will be coded using the WHO Drug Dictionary [Version B2-DDE March 2016 (or a later version if updated during the study)], Anatomical Therapeutic Chemical (ATC) Classification codes.

Prior medications and concomitant medications are defined as follows:

- Prior medications are those taken with a start date prior to the first dose date of study treatment
- Concomitant medications are those with a start date on or after the first dose date of study treatment, or those with a start date before the first dose date of study treatment and a

stop date on or after the first dose date of study treatment (including those medications which are classified as ongoing).

If a medication cannot be classified as “prior” or “concomitant” after applying imputation rules for missing/incomplete dates, it will be classified as concomitant.

Prior medications, prohibited medications (refer to protocol sections 6.4 and 7.8) and concomitant medications taken during the study will be summarized for the mITT population. The number and percentage of subjects using each medication will be summarized by ATC-Level 2 class and preferred term by treatment group.

Prohibited medications include PPAR γ agonists, insulin, ursodeoxycholic acid, paclitaxel, phenytoin, warfarin, celecoxib, tolbutamide and repaglinide. A disallowed change post-randomization in dose of metformin, GLP1 agonists, SGLT2 inhibitors, sulfonylureas, DPP4 inhibitors, or insulin will be included in the summary of prohibited concomitant medications.

The number and percentage of diabetic subjects (subjects with T2DM) with an up-titration, down-titration, and no major change in glycemic control medications after randomization will also be summarized by treatment group. The classification of each subject into one of the three categories will be based on blinded adjudication based on a manual review of subjects’ use of glycemic control medications prior to final database lock and unblinding. The “no major change” category may include subjects with changes identified as not being clinically significant during blinded adjudication.

In addition, all prior and/or concomitant medications will be presented in subject data listings, with additional listings presenting only prohibited medications and only glycemic control medications.

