7.8.4 Exploratory Analysis

Exploratory efficacy endpoints are listed in Section 3.3.

The analysis of mean change from baseline at 12 months in liver stiffness will be restricted to subjects for whom liver stiffness has been measured using the FibroScan device. The type of device for each subject and time-point was not recorded in the eCRF but will be captured in an external spreadsheet and provided by the Sponsor prior to unblinding for the final analysis.

All exploratory analysis will be performed for the mITT population. For change from baseline endpoints, baseline values, post-baseline values, and change from baseline will be summarized by treatment groups at each evaluation time point. Highly skewed variables will be log-transformed for analysis, and geometric mean changes presented. Comparisons between each active dose and placebo will be done using ANCOVA models for continuous variables, similarly as for secondary endpoints (refer to Section 7.8.2). Regardless of skewness, summaries and ANCOVA results will be presented for log-transformed values of ALT, AST, ALP, and GGT, in addition to results based on non-transformed values.

Fibrosure numeric results (rather than results expressed as fibrosis stage) will be analyzed. Changes in diagnostic category (NASH diagnosis confirmed or cannot be confirmed) from baseline to month 12 will be presented by means of a shift table.

Changes in markers of insulin sensitivity (HOMA-IR, HbA1c, fasting plasma glucose, and fasting insulin) will be analyzed overall and then separately in subjects with T2DM, and in subjects with T2DM without a major up- or down-titration in glycemetic control medications during the study (categorized into the “no major change” category during blinded adjudication).

Mean change from baseline with standard error bars will be plotted for each treatment group by visit for insulin sensitivity markers (HOMA-IR, HbA1c, fasting plasma glucose, and fasting insulin) in the mITT population for (1) subjects with T2DM, and (2) subjects with T2DM without major changes in their glycemetic control medications during the study.

Normalization of ALT and AST will be evaluated with shift tables presenting movement in and out of reference range from baseline to each scheduled post-baseline visit as defined in Section 7.9.2 and will be provided for each treatment group in the mITT population.

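### The SAP's 6-month medication-change analyses of the exploratory glycemic markers ignore whether the drug change came before or after the 6-month sample

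*SAP*

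**What the plan says.** SAP 7.6 sorts diabetic subjects into up-titration, down-titration or no major change. The period that counts is everything after randomization ("control medications after randomization will also be summarized by treatment group"). There is one label per subject: "The classification of each subject into one of the three categories will be based on blinded adjudication", made by manual review before final database lock. No date enters the label.

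The label is used in two places.

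- **SAP 6.2.4 (HbA1c).** If more than 35% of up-titrated subjects are on placebo, a sensitivity analysis may be run "where the 6- and 12-month values of HbA1c for subjects who had a major up-titration of glycemic control medications will be imputed" as 0.5% "higher than the observed value". A mirror rule subtracts 0.5% for down-titrated subjects when more than 15% of them are on placebo.
- **SAP 7.8.4.** HOMA-IR, HbA1c, fasting glucose and fasting insulin are analyzed overall, in all diabetic subjects, and in "subjects with T2DM without a major up- or down-titration in glycemetic control medications during the study". The last group also has its own by-visit plots and its own HbA1c shift tables to 6 and to 12 months.

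The opening sentence on HbA1c in 6.2.4 makes these analyses depend on how medication changes are distributed "between the placebo and active treatment groups at 6 and 12 months". The rule for missing HbA1c in the same section is explicitly per time point ("separately at 6 and 12 months) are in the placebo group"). The two titration rules carry no such words.

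**The concern.** A drug change cannot affect a sample drawn before it. Under the text as written, a change made at any time after randomization alters or removes the 6-month value as well as the 12-month one.

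This matters most if the later change was prompted by the 6-month result. Dropping such subjects then selects on the very outcome being analyzed: it removes high 6-month values, and more of them from placebo if placebo subjects are up-titrated more often. Adding 0.5% to the same values pushes the other way. A reader would turn to these analyses to learn whether medication changes distort the glycemic effect, and at 6 months they could add distortion of their own.

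**Working it through.** The plan gives no figure for this point, so there is none to reproduce. The first step traces the text; the others show size under stated assumptions.

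**1. One subject traced through the rules.** Suppose a diabetic subject has the 6-month sample on Day 180 and a first major up-titration on Day 220.

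| Analysis | 6-month value |
|---|---|
| Overall and all-diabetic (7.8.4) | kept as observed |
| +0.5% sensitivity analysis (6.2.4), if run; HbA1c only | raised by 0.5, though drawn 40 days before the change |
| No-major-change subset, its plots and HbA1c shift table (7.8.4) | excluded |

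**2. The +0.5% rule.** Let u_P and u_A be the proportions of diabetic subjects up-titrated on placebo and on each active arm, and q the share of those changes made after the 6-month sample. The spurious 6-month shift (active minus placebo; negative favors active) is

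−0.5 × q × (u_P − u_A).

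With 1:1:1:1 allocation, the placebo share of up-titrated subjects is u_P / (u_P + 3u_A). It passes 35% once u_P/u_A exceeds 3 × 0.35/0.65 = 1.6. So the analysis is triggered only when up-titration is commoner on placebo. All rates below are assumed.

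| u_P / u_A | Placebo share | q = 0.25 | q = 0.5 | q = 1 |
|---|---|---|---|---|
| 10% / 5% | 40% | −0.006 | −0.013 | −0.025 |
| 20% / 10% | 40% | −0.013 | −0.025 | −0.050 |
| 30% / 15% | 40% | −0.019 | −0.038 | −0.075 |
| 30% / 10% | 50% | −0.025 | −0.050 | −0.100 |

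Example: −0.5 × 0.5 × (0.20 − 0.10) = −0.025 HbA1c percentage points.

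**3. The exclusion rule.** Suppose all changes are late (q = 1) and relate to the 6-month value with correlation ρ. With a proportion f removed and z the (1 − f) normal quantile, the mean of those retained moves by −ρ × φ(z)/(1 − f) SD. For ρ = 0.5, f = 0.20 gives −0.175 and f = 0.10 gives −0.097. The bias (active minus placebo) is −0.097 − (−0.175), about +0.08 SD, against active.

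| u_P / u_A | ρ = 0.3 | ρ = 0.5 | ρ = 1.0 |
|---|---|---|---|
| 10% / 5% | +0.026 | +0.043 | +0.086 |
| 20% / 10% | +0.046 | +0.077 | +0.155 |
| 30% / 15% | +0.067 | +0.111 | +0.222 |
| 30% / 10% | +0.091 | +0.151 | +0.302 |

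Take the SD as 0.6 to 0.8 HbA1c points (assumed). Then ρ of 0.3 to 0.5 gives 0.026 × 0.6 = 0.02 up to 0.151 × 0.8 = 0.12 points. The extreme corner (ρ = 1, 30% / 10%) gives 0.302 × 0.8 = 0.24.

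**4. If only the protocol's suggested rescue drove changes.** Protocol 6.4 suggests rescue when HbA1c exceeds 9.5% at two consecutive visits. With an assumed mean of 7.2% and SD of 0.9, (9.5 − 7.2)/0.9 = 2.56, so about 0.5% of subjects exceed 9.5% on one reading. Even with none on active, the +0.5% rule then shifts the difference by only 0.5 × 0.005 = 0.0025 points.

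**5. After the fix.** If a change counts at Month 6 only when it precedes the 6-month sample, the part of both biases that comes from later changes is zero by construction.

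**The case against.** **Scope.** A reader might infer that the 6-month glycemic comparisons in general are biased. The documents do not support that. The overall and all-diabetic analyses use observed values and exclude nobody for a drug change. The HbA1c adjustment is conditional and optional ("a sensitivity analysis may be done where the 6- and 12-month values of HbA1c for subjects who had a major up-titration"). Altering values concerns HbA1c only; the other three markers are touched only through the subset. Everything affected is exploratory. All of this stands.

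**Schedule.** A reader might also infer that most up-titrations must follow the Day 180 result because HbA1c and fasting glucose are measured on treatment only at Days 180 and 360. Protocol 7.5 and footnote 10 of Table 1 point that way. But Table 2 lists HbA1c under hematology and fasting glucose under chemistry, and Table 1 schedules both panels at every visit. These passages need reconciling, and the inference cannot be stated as fact. Protocol 6.4 also leaves diabetes care to the subject's own healthcare provider, who may act earlier. Late, result-driven changes are plausible but not established.

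**Wording.** The opening of 6.2.4 could be read as judging changes at each time point. It describes when the distribution is examined, however. No per-time-point category is defined anywhere, and the missing-data rule beside it shows that the authors wrote the restriction where they wanted it. The ambiguity itself calls for a clarification.

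**Fixed subset.** One study-wide no-change group follows the same subjects across visits in the plot. That is a genuine advantage, and the fix gives it up.

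**Conclusion.** The point holds for a limited set of analyses: the optional HbA1c titration sensitivity analyses in SAP 6.2.4, and the planned no-major-change diabetic subset in 7.8.4 with its plots and HbA1c shift tables. Followed literally, the text alters or discards valid 6-month values because of drug changes made later.

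The direction depends on two assumptions: that later up-titration follows high 6-month values, and that it is commoner on placebo. Then the subset tends to understate the 6-month effect and the +0.5% rule to overstate it. The size cannot be derived from the documents, which give no titration rates. Under the assumed rates it is mostly about 0.01 to 0.1 HbA1c percentage points, near zero if changes are as rare as the rescue threshold alone might imply, and larger only with very strong selection. The primary and secondary histology endpoints, the sample size and the main 6-month glycemic analyses are unaffected. It is worth correcting because the rule is wrong at 6 months as stated and the remedy is cheap.

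**What to change.** - **SAP 7.6:** have the blinded adjudication record the date of each major change, and classify each diabetic subject twice: for changes before the 6-month sample and for changes before the 12-month sample. Use the actual sample date, not the nominal day. Say how a change on the sample date is counted; one made after the draw at that visit belongs to the next time point. SAP 6.2.1 limits imputed medication dates to separating prior from concomitant use, so also say how the adjudicators place a partial date.
- **SAP 6.2.4:** add or subtract 0.5% only for an HbA1c drawn after the change, and assess the 35% and 15% triggers separately at each time point.
- **SAP 7.8.4:** define the no-major-change group at each time point as having no major change before that sample, for the models, plots and shift tables.

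The cost is a few sentences and a date field in a review already planned under blinding. The no-change subset will differ between 6 and 12 months, so the by-visit plot no longer follows one fixed group and should say so. No clinical rule, sample size or primary analysis changes.
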